6.1 Inclusion Criteria

- 0.1.** Participants must have signed and dated an IRB/IEC approved written informed consent form in accordance with regulatory and institutional guidelines. This must be obtained before the performance of any protocol-related procedures that are not part of normal patient care.
- 0.2.** Participant must be willing and able to comply with scheduled visits, treatment schedule, laboratory tests, and other requirements of the study.
- 0.3.** Participant must be 18 years of age or older
- 0.4.** Participants with pathologically confirmed grade 2, 3 or 4 gliomas with IDH mutation (confirmed by IDH R132H immunohistochemistry or IDH1/IDH2 next generation sequencing) who have progressive tumor and have had previous exposure to alkylating agents.
- 0.5.** Participants must have measurable disease, defined as at least one enhancing tumor lesion that can be accurately measured in at least one dimension as $\geq 10\text{mm} \times 10\text{mm}$ on brain MRI. See 13.2 Disease Parameters for more information regarding evaluation of measurable disease. Patients with non-enhancing measurable disease may be eligible upon discussion with and approval by the CUMC PI.
- 0.6.** Documentation of availability of sufficient baseline tumor for analysis, defined as a minimum of 20 unstained slides or equivalent quantity of frozen tumor or FFPE tumor block.
- 0.7.** KPS of 60 and above
- 0.8.** Adequate bone marrow, kidney and liver function as defined below:
 - i) White blood count (WBC) $\geq 3000/\mu\text{L}$

Columbia University Medical Center
Herbert Irving Comprehensive Cancer Center
Version Date: January 30, 2024

- ii) Neutrophils $\geq 1500/\mu\text{L}$
- iii) Absolute lymphocyte count $\geq 500/\mu\text{L}$
- iv) Platelets $\geq 100 \times 10^3/\mu\text{L}$
- v) Hemoglobin $\geq 9.0\text{g/dL}$
- vi) Serum creatinine $\leq 1.5 \times$ upper limit of normal (ULN) or calculated creatinine clearance $> 50 \text{ mL/min}$ (using the Cockcroft-Gault formula)

1.9. Female CrCl = $(140 - \text{age in years}) \times \text{weight in kg} \times 0.85 \times 72 \times \text{serum creatinine in mg/dL}$

2.10. Male CrCl = $(140 - \text{age in years}) \times \text{weight in kg} \times 1.00 \times 72 \times \text{serum creatinine in mg/dL}$

2.11. vi) Aspartate aminotransferase (AST) and alanine aminotransferase (ALT) $\leq 3.0 \times \text{ULN}$

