3.12. vii) Total bilirubin (TBIL) $\leq 1.5 \times \text{ULN}$ (except participants with Gilbert Syndrome who must have a total bilirubin level of $< 3.0 \times \text{ULN}$)

6.13. Women of childbearing potential (WOCBP) must have a negative serum or urine pregnancy test (minimum sensitivity 25 IU/L or equivalent units of human chorionic gonadotropin) within 24 hours prior to the start of study drug

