6.2 Exclusion Criteria

0.1. Participants with an active, known, or suspected autoimmune disease.

0.2. Participants with type I diabetes mellitus, hypothyroidism only requiring hormone replacement, skin disorders (such as vitiligo, psoriasis, or alopecia) not requiring systemic treatment, or conditions not expected to recur in the absence of an external trigger are permitted to enroll.

6.3. Participants with a condition requiring systemic treatment with either corticosteroids (> 10 mg daily prednisone equivalent) or other immunosuppressive medications within 14 days of start of study treatment. Inhaled or topical steroids, and adrenal replacement steroid doses > 10 mg daily prednisone equivalent, are permitted in the absence of active autoimmune disease. Dose of dexamethasone ≤ 4 mg/day or equivalent is allowed at the study entry for brain tumor edema.^{35,36} Participants are permitted the use of topical, ocular, intra-articular, intranasal, and inhalational corticosteroids (with minimal systemic absorption). A brief (less than 3 weeks) course of corticosteroids for prophylaxis (eg, contrast dye allergy) or for treatment of non-autoimmune conditions (eg, delayed-type hypersensitivity reaction caused by a contact allergen) is permitted. Participants who have received chemotherapy or experimental agents within 4 weeks (except for 6 weeks for nitrosoureas and 23 days for temozolomide) and radiotherapy within 12 weeks of the first dose of the study treatment.

6.4. Prior use of PD-1, PD-L1, or CTLA-4 inhibitors or exposure to other checkpoint inhibitors.

6.5. Prior exposure to bevacizumab or other VEGF or VEGFR inhibitors.

6. Any positive test for hepatitis B virus or hepatitis C virus indicating acute or chronic infection, and/or detectable virus

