9 DOSING DELAYS/DOSE MODIFICATIONS

Dose Modifications for Nivolumab

Dose modifications are not allowed for nivolumab.

Dose Delay Criteria for Nivolumab

Tumor assessments should continue per protocol schedule, even if dosing is delayed. Treatment delays will be recorded, but the total duration of therapy will be up to two years, regardless of the number of cycles. Nivolumab administration should be delayed for the following:

- Any Grade ≥ 2 non-skin, drug-related AE, with the following exception:
 - Grade 2 drug-related fatigue or laboratory abnormalities do not require a treatment delay
- Grade 2 drug-related creatinine, AST, ALT, or TBILI abnormalities
- Any Grade 3 skin, drug-related AE
- Any Grade 3 drug-related laboratory abnormality (excluding AST, ALT, or TBILI), with the following exceptions for lymphopenia or asymptomatic amylase or lipase:
 - Grade 3 lymphopenia does not require dose delay
 - Any Grade ≥ 3 drug-related amylase or lipase abnormality that is not associated with symptoms or clinical manifestations of pancreatitis does not require dose delay
- Any AE, laboratory abnormality, or intercurrent illness which, in the judgment of the investigator, warrants delaying the dose of study medication [L]
[SEP]

Participants who require delay of nivolumab should be re-evaluated weekly or more frequently if clinically indicated, and resume nivolumab dosing when re-treatment criteria are met.

Criteria to Resume Dosing for Nivolumab

Participants may resume treatment with study drug when the drug-related AE(s) resolve to Grade ≤ 1 or baseline value, with the following exceptions:

- Participants may resume treatment in the presence of Grade 2 fatigue.
- Participants who have not experienced a Grade 3 drug-related skin AE may resume treatment in the presence of Grade 2 skin toxicity.
- For participants with Grade 2 AST, ALT, or TBILI elevations, dosing may resume when laboratory values return to baseline and management with corticosteroids, if needed, is complete.
- Participants with combined Grade 2 AST/ALT AND TBILI values meeting discontinuation parameters should have treatment permanently discontinued.

Columbia University Medical Center
Herbert Irving Comprehensive Cancer Center
Version Date: January 30, 2024

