- Drug-related pulmonary toxicity, diarrhea, or colitis must have resolved to baseline before treatment is resumed. Participants with persistent Grade 1 pneumonitis after completion of a steroid taper over at least 1 month may be eligible for retreatment.
- Participants with drug-related endocrinopathies adequately controlled with only physiologic hormone replacement may resume treatment after consultation with the principal investigator.

Recommended Dose Modifications for Nivolumab

Event	Severity*	Dose modification
Colitis	Grade 2 or 3 diarrhea or colitis	Withhold dose ^a
	Grade 4 diarrhea or colitis	Permanently discontinue
Pneumonitis	Grade 2 pneumonitis	Withhold dose ^a
	Grade 3 or 4 pneumonitis	Permanently discontinue
Hepatitis	Aspartate aminotransferase (AST)/or alanine aminotransferase (ALT) more than 3 and up to 5 times the upper limit of normal or total bilirubin more than 1.5 and up to 3 times the upper limit of normal	Withhold dose ^a
	AST or ALT more than 5 times the upper limit of normal or total bilirubin more than 3 times the upper limit of normal	Permanently discontinue
Hypophysitis	Grade 2 or 3 hypophysitis	Withhold dose ^a
	Grade 4 hypophysitis	Permanently discontinue
Adrenal insufficiency	Grade 2 adrenal insufficiency	Withhold dose ^a
	Grade 3 or 4 adrenal insufficiency	Permanently discontinue
Type 1 Diabetes Mellitus	Grade 3 hyperglycemia	Withhold dose ^a
	Grade 4 hyperglycemia	Permanently discontinue
Nephritis and renal dysfunction	Serum creatinine more than 1.5 and up to 6 times the upper limit of normal	Withhold dose ^a
	Serum creatinine more than 6 times the upper limit of normal	Permanently discontinue
Skin	Grade 3 rash or suspected Stevens-Johnson syndrome (SJS) or toxic epidermal necrolysis (TEN)	Withhold dose ^a
	Grade 4 rash or confirmed SJS or TEN	Permanently discontinue
Encephalitis	New-onset moderate or severe neurologic signs or symptoms	Withhold dose ^a
	Immune-mediated encephalitis	Permanently discontinue
Other	Other Grade 3 adverse reaction: 1. First occurrence 2. Recurrence of same Grade 3 adverse reactions	1. Withhold dose ^a 2. Permanently discontinue
	Life threatening or Grade 4 adverse reaction	Permanently discontinue

Columbia University Medical Center
Herbert Irving Comprehensive Cancer Center
Version Date: January 30, 2024

	Requirement for 10 mg per day or greater prednisone or equivalent for more than 12 weeks	Permanently discontinue

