	Persistent Grade 2 or 3 adverse reactions lasting 12 weeks or longer	Permanently discontinue

*Toxicity was graded per National Cancer Institute Common Terminology Criteria for Adverse Events. Version 4.0 (NCI CTCAE v4).

^a Resume treatment when adverse reaction returns to Grade 0 or 1.

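### For participants admitted through the bilirubin and creatinine exceptions in 6.1, the Section 9 table and the Section 9 text give conflicting rules on withholding and restarting nivolumab

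*Combined protocol and SAP*

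**What the plan says.** **Eligibility (Section 6.1).** Total bilirubin must be at most 1.5 × ULN, "except participants with Gilbert Syndrome who must have a total bilirubin level of" less than 3.0 × ULN. Renal function is an either/or criterion: creatinine at most 1.5 times the "upper limit of normal (ULN) or calculated creatinine clearance" above 50 mL/min by Cockcroft-Gault. The clearance branch sets no ceiling on creatinine.

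**Section 9, table of recommended dose modifications.** The Hepatitis row withholds for "total bilirubin more than 1.5 and up to 3 times the upper limit of normal". The Nephritis and renal dysfunction row withholds for "Serum creatinine more than 1.5 and up to 6 times the upper limit of normal". Footnote a, attached to both, reads "Resume treatment when adverse reaction returns to Grade 0 or 1". A later row permanently discontinues for Grade 2 or 3 adverse reactions that persist for 12 weeks or more.

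**Section 9, text before the table.** Delay applies to Grade 2 creatinine, AST, ALT or bilirubin abnormalities that are drug-related. On restart: "Participants may resume treatment with study drug when the drug-related AE(s) resolve to Grade" 1 or lower, or to the baseline value. For Grade 2 AST, ALT or bilirubin elevations there is a specific clause: "dosing may resume when laboratory values return to baseline and management with corticosteroids, if needed, is complete".

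**The concern.** One section holds two sets of rules. The text ties the trigger to the drug and accepts the participant's own baseline as an endpoint for restart. The table gives absolute multiples of ULN and an absolute grade.

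For a participant who enters under the ordinary limits the difference seldom matters, because the baseline lies below the withhold band. For a participant admitted under one of the 6.1 exceptions the baseline can already lie inside the band. The table and the text can then lead to opposite dosing actions on the same laboratory value. Section 12.2 requires chemistry within 72 hours of dosing from Cycle 2 onward, so the question can recur at every cycle.

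At stake is whether participants whom the protocol deliberately admits are treated as intended, and in the same way at all three sites.

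**Working it through.** The plan states no figure on this point, so the check compares thresholds.

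**Step 1: eligible ranges against withhold bands**

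| Measure | Eligible range (6.1) | Withhold band (Section 9 table) | Overlap |
|---|---|---|---|
| Bilirubin, general | ≤1.5 × ULN | >1.5 to 3 × ULN | none; the limits abut |
| Bilirubin, Gilbert syndrome | <3.0 × ULN | >1.5 to 3 × ULN | >1.5 to <3.0 × ULN |
| Creatinine, first branch | ≤1.5 × ULN | >1.5 to 6 × ULN | none; the limits abut |
| Creatinine, clearance branch | no ceiling if clearance >50 mL/min | >1.5 to 6 × ULN | possible; see step 2 |
| AST/ALT | ≤3.0 × ULN | >3 to 5 × ULN | none; the limits abut |

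Every bilirubin value that the Gilbert exception adds lies inside the withhold band.

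**Step 2: can the clearance branch reach the creatinine band?** Cockcroft-Gault is clearance = (140 − age) × weight × f / (72 × creatinine), with f = 1.00 for men and 0.85 for women. The formula in 6.1 prints without its fraction bar, which I take to be an artefact of text extraction. The documents give no ULN for creatinine; I assume 1.2 mg/dL and vary it from 1.0 to 1.3.

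Worked case, a man of 40 years and 80 kg with creatinine 1.92 mg/dL:
- clearance = (140 − 40) × 80 / (72 × 1.92) = 8000 / 138.24 = 57.9 mL/min, above 50, so eligible;
- 1.92 / 1.2 = 1.6 × ULN, so inside the withhold band.

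The highest eligible creatinine is just below (140 − age) × weight × f / (72 × 50). At ULN 1.2 mg/dL and 80 kg:

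| Participant | Creatinine at clearance 50 | As multiple of ULN | Overlap with >1.5 × ULN |
|---|---|---|---|
| Man, 30 | 110 × 80 / 3600 = 2.44 mg/dL | 2.04 | yes |
| Man, 45 | 95 × 80 / 3600 = 2.11 mg/dL | 1.76 | yes |
| Woman, 30 | 110 × 80 × 0.85 / 3600 = 2.08 mg/dL | 1.73 | yes |
| Man, 60 | 80 × 80 / 3600 = 1.78 mg/dL | 1.48 | no |

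For the man of 30 the limit is 2.44, 2.04 and 1.88 × ULN at ULN 1.0, 1.2 and 1.3. The overlap is real for younger or heavier participants. It vanishes for many older or lighter ones.

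**Step 3: apply both rules to the same participant.** Take a Gilbert participant with an eligible baseline of 2.0 × ULN (illustrative).
- *Bilirubin unchanged at 2.0.* Text: no drug-related abnormality, so no delay. Table, read literally: the value is in the withhold band. Footnote a cannot be met at baseline, and the 12-week persistence row could follow.
- *Drug-related rise, then return to 2.0.* Text: restart is allowed, because the value is back at baseline and any corticosteroid management is complete. Footnote a: no restart, because the value is still above Grade 1.

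The documents do not print the CTCAE cut-offs. I assume that values above 1.5 × ULN exceed Grade 1, which fits the way the Section 9 text and table are built. The creatinine case runs the same way, except that the restart at baseline then comes from the general clause of the text.

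**The case against.** The strongest reply is that the table should be read with the text. Its rows are headed by events (hepatitis, nephritis), its footnote speaks of an adverse reaction, and resuming presupposes that treatment has begun. Section 10.4 records a pre-existing condition as an adverse event only if it worsens. A stable Gilbert bilirubin is then neither hepatitis nor an adverse reaction, and the table is in any case headed as recommended.

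Much of this stands. A reader might infer that an eligible participant must be withheld before the first infusion, or can never meet a restart rule. The documents do not support either. A withhold before the first dose needs a literal reading of the numeric bands, and the text offers restart at baseline. Only footnote a lacks that route.

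The reply does not remove the conflict. The table does qualify triggers elsewhere: the Encephalitis row requires new onset or an immune-mediated cause. The bilirubin and creatinine cells carry no such words, and renal dysfunction is not confined to immune-mediated disease. In the second case of step 3 the event is a drug-related reaction on any reading, and the two restart rules still disagree. Nothing in Section 9 says which takes precedence.

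**Conclusion.** The point holds as an internal contradiction in Section 9, limited to participants admitted through the Gilbert exception or the creatinine-clearance branch. It is minor. The number affected is probably small, and the documents do not allow a count. For scale only, if 3% to 10% of participants had Gilbert syndrome (assumption), that would be 0.03 × 37 = 1.1 to 0.10 × 37 = 3.7 participants, and only those above 1.5 × ULN would be touched. The result also rests on the assumed creatinine ULN (1.0 to 1.3 mg/dL) and on values above 1.5 × ULN exceeding Grade 1.

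Four further inferences might be drawn, and the documents do not support them:
- *That undosed participants count as non-responders.* Section 13.1.1 requires at least one cycle for evaluability, and 15.7 allows those who received no study drug to be left out.
- *That each affected participant costs 3 points of ORR.* The figure 1/33 = 3.0 points is a maximum for a participant certain to respond. At the plan's own rates the expected loss is 0.30/33 = 0.9 or 0.10/33 = 0.3 points, and only if the participant is in the analysis.
- *That the diabetes row has the same overlap.* Section 6.2 permits "Participants with type I diabetes mellitus, hypothyroidism only requiring hormone replacement", but neither 6.1 nor 6.2 sets a glucose range, so no eligible baseline is shown to lie in the hyperglycemia bands.
- *That the combined AST/ALT and bilirubin rule in 8.5 is met at entry.* It needs AST or ALT above 3 × ULN, and 6.1 caps both at 3.0.

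**What to change.** Reconcile the Hepatitis and Nephritis rows and footnote a of the Section 9 table with Section 6.1 and the Section 9 text. For each row, state whether the trigger is an absolute level or a drug-related change from the participant's baseline. State the same for restart, and say how participants admitted above 1.5 × ULN under the two exceptions are handled. The medical lead decides which rule applies; this review proposes none.

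The cost is a wording amendment to two table rows and one footnote. No extra tests are needed, because bilirubin and creatinine are already measured at screening (Section 12.1).

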8.5 Criteria for Removal from Study Drug

Participants will be removed from study when any of the criteria listed below or in section 6.9 applies. The reason for study removal and the date the participant was removed will be documented in the Case Report Form.

Treatment Discontinuation Criteria for Nivolumab

Nivolumab treatment should be permanently discontinued for the following:

- Any Grade 2 drug-related uveitis, eye pain, or blurred vision that does not respond to topical therapy and does not improve to Grade 1 severity OR requires systemic treatment
- Any Grade 3 non-skin, drug-related AE lasting > 7 days, with the following exceptions for laboratory abnormalities, drug-related uveitis, pneumonitis, bronchospasm, hypersensitivity reactions, infusion reactions, and endocrinopathies:
 - Grade 3 drug-related uveitis, pneumonitis, bronchospasm, hypersensitivity reaction, or infusion reaction of any duration requires discontinuation [SEP]
 - Grade 3 drug-related endocrinopathies adequately controlled with only physiologic hormone replacement do not require discontinuation [SEP]
 - Grade 3 drug-related laboratory abnormalities do not require treatment discontinuation except:
 - Grade 3 drug-related thrombocytopenia > 7 days or associated with bleeding requires discontinuation
 - Grade >3 drug-related AST, ALT, or TBILI requires discontinuation*
 - Concurrent AST or ALT > 3xULN and TBILI > 2xULN [SEP]

* In most cases of Grade 3 AST or ALT elevation, study drug(s) will be permanently discontinued. If the investigator determines a possible favorable benefit/risk ratio that warrants

continuation of study drug(s), a discussion between the principal investigator and the treating physician must occur.

- Any Grade 4 drug-related AE or laboratory abnormality, except for the following events which do not require discontinuation:
 - Grade 4 neutropenia \leq 7 days
 - Grade 4 lymphopenia or leukopenia
 - Isolated Grade 4 amylase or lipase abnormalities that are not associated with symptoms or clinical manifestations of pancreatitis
 - Isolated Grade 4 electrolyte imbalances/abnormalities that are not associated with clinical sequelae and are corrected with supplementation/appropriate management within 72 hours of their onset

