 - Grade 4 drug-related endocrinopathy AEs, such as adrenal insufficiency, ACTH deficiency, hyper- or hypothyroidism, or glucose intolerance, which resolve or are adequately controlled with physiologic hormone replacement (corticosteroids, thyroid hormones) or glucose-controlling agents, respectively, may not require discontinuation after discussion with and approval from the principal investigator
- Any event that leads to delay in dosing lasting $>$ 8 weeks from the previous dose requires discontinuation, with the following exceptions:
 - Dosing delays to allow for prolonged steroid tapers to manage drug-related AEs are allowed. Tumor assessments should continue as per protocol even if dosing is delayed. Periodic study visits to assess safety and laboratory studies should also continue every 6 weeks or more frequently if clinically indicated during such dosing delays.
 - Dosing delays lasting $>$ 8 weeks from the previous dose that occur for non-drug-related reasons may be allowed if approved by the principal investigator. Prior to re-initiating treatment in a participant with a dosing delay lasting $>$ 8 weeks, the principal investigator must be consulted. Tumor assessments should continue as per protocol even if dosing is delayed. Periodic study visits to assess safety and laboratory studies should also continue every 6 weeks or more frequently if clinically indicated during such dosing delays.
- Any AE, laboratory abnormality, or intercurrent illness which, in the judgment of the investigator, presents a substantial clinical risk to the participant with continued nivolumab dosing

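### Nivolumab stopping instructions conflict in three places (Section 8.5 against the Section 9 table in both directions, and 11.2 against 13.3), and no sentence ranks the sections

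*Combined protocol and SAP*

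**What the plan says.** **Toxicity, Section 8.5.** Nivolumab ends permanently for "Any Grade 3 non-skin, drug-related AE lasting > 7 days". The exceptions cover laboratory abnormalities, endocrinopathies and a group that is handled more strictly: "Grade 3 drug-related uveitis, pneumonitis, bronchospasm, hypersensitivity reaction, or infusion reaction of any duration requires discontinuation". Colitis is not among the exceptions. For hormone disorders the section says "Grade 3 drug-related endocrinopathies adequately controlled with only physiologic hormone replacement do not require discontinuation", and Grade 4 endocrinopathies that resolve or are adequately controlled "may not require discontinuation after discussion with and approval from the principal investigator". Under stated conditions it also exempts Grade 4 neutropenia, lymphopenia or leukopenia, and isolated amylase, lipase or electrolyte abnormalities.

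**Toxicity, Section 9.** The closing table, headed as recommended modifications, withholds the dose for "Grade 2 or 3 diarrhea or colitis" and for "Other Grade 3 adverse reaction: 1. First occurrence". It stops treatment permanently on recurrence of the same Grade 3 reaction, or when a Grade 2 or 3 reaction has persisted for 12 weeks. It also stops permanently for "Grade 3 or 4 adrenal insufficiency", Grade 4 hypophysitis, Grade 4 hyperglycemia and, in a general row, any life-threatening or Grade 4 reaction. None of these rows carries an exception. The resumption criteria just above the table let a participant whose endocrinopathy is controlled on physiologic replacement restart after the principal investigator is consulted.

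**Progression.** Section 11.2 permits dosing after a first progression if four conditions are met: clinical benefit, tolerance, no delay to an urgent intervention, and fresh written consent. It permits it again if a scan within 8 weeks still shows progression, until a second scan within a further 8 weeks. It sets no limit by time since starting therapy. Section 13.3 says participants with progression more than 6 months from the start should discontinue. Earlier progression may be confirmed over up to 3 months, and participants confirmed as progressing should then stop.

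**Cross-references.** The mandatory list in Section 6.9 refers to 8.5 for toxicity and names 13.3 as the exception for progression. It mentions neither the table nor 11.2. Section 8.1 sends the reader to Section 9 for dose modifications.

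**The concern.** A physician who follows the table or Section 11.2 exactly can dose a participant whom 8.5 or 13.3 says should stop. For safety the laxer direction matters most. A participant with Grade 3 colitis lasting more than a week must come off for good under 8.5, but under Section 9 may be dosed again once recovered.

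In the stricter direction the cost is lost treatment. A participant with controlled Grade 3 adrenal insufficiency would be stopped by the table although 8.5 would let dosing continue.

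The trial has three sites, and monitors must judge compliance with the protocol. With two live instructions, the same rechallenge can be read as compliant or as a deviation.

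**Working it through.** The point rests on comparing rules, so the plan has no figure of its own to reproduce here. The inputs are Sections 6.9, 8.1, 8.2, 8.5, 9, 11.2 and 13.3.

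| Situation | Instruction A | Instruction B |
|---|---|---|
| Grade 3 colitis, more than 7 days | 8.5: stop permanently | Table: withhold |
| First other Grade 3 non-skin reaction, more than 7 days, not excepted in 8.5 | 8.5: stop permanently | Table: withhold |
| First Grade 3 uveitis, bronchospasm or hypersensitivity | 8.5: stop at any duration | Table: not named, so falls in the other-Grade-3 row and is withheld |
| First Grade 3 infusion reaction | 8.2 and 8.5: stop permanently | Table: not named; only the table is out of line |
| Grade 3 adrenal insufficiency controlled on physiologic replacement | 8.5: need not stop; Section 9 text: may resume after consultation | Table: stop permanently |
| Grade 4 events excepted in 8.5 | 8.5: no stop required, or none with investigator approval | Table, including the general Grade 4 row: stop permanently |
| Progression more than 6 months from start | 13.3: should discontinue | 11.2: may continue if conditions are met |
| Progression within 6 months | 13.3: up to 3 months to confirm, then should discontinue | 11.2: may continue past a first continued-progression scan |

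Grade 3 pneumonitis is a permanent stop in both places, so it is not in conflict.

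**Size, toxicity.** The table's persistence limit is 12 × 7 = 84 days, and the limit in 8.5 is 7 days. A first Grade 3 colitis, or another first Grade 3 reaction that 8.5 does not except, is therefore a permanent stop in 8.5 and a hold in the table if it lasts 8 to 83 days. The difference of 84 − 7 = 77 days is time with the drug withheld. It is not 77 days of extra exposure.

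**Size, progression.** Section 11.2 allows 8 + 8 = 16 weeks after first progression. Three months is 3 × (365.25 / 12) / 7 = 13.0 weeks.
- Within the first 6 months, 11.2 runs past the confirmation window by at most about 16 − 13 = 3 weeks.
- After 6 months, 13.3 offers no confirmation window, against up to about 16 weeks in 11.2.

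**Effect on the design.** With 33 evaluable participants and success at 7 or more responses, the exact one-sided alpha is 0.0417 at a 10% response rate and power is 0.906 at 30%. Inflating for 10% unevaluable gives 33 / 0.9 = 36.7, rounded up to 37. The plan's 33 and 37 reproduce, and no stopping rule enters either calculation.

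**The case against.** The strongest reply is that the protocol already leans one way. Section 6.9 is a mandatory list that sends toxicity to 8.5, Section 8.5 applies when any of its criteria is met, and the table is only a recommendation. On that reading the 7-day stop applies whatever the table withholds. This has force, and it shows which way the fix should go. It remains a pointer: 6.9 mentions neither the table nor 11.2, and 8.1 directs readers to Section 9. Nor can a ranking of sections repair Section 9's disagreement with itself over controlled adrenal insufficiency. Always taking the stricter rule would resolve the conflicts, but the protocol does not say to do so, and it would remove the continuation that 8.5 expressly allows.

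On progression, the iRANO text in 13.3 is introduced as guidance and says should, while 11.2 is the dosing section and sets conditions. That softens the clash. However, the stop after confirmed progression stands in the RANO criteria ahead of that introduction, and 6.9 names 13.3 alone as the exception. The 6-month rule is also absent from the low-grade criteria in 13.4, so it does not reach participants with only non-enhancing lesions.

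A reader might infer more than the documents support:
- *That a first Grade 3 infusion reaction could be re-dosed.* Section 8.2 separately requires permanent discontinuation.
- *That colitis could be re-dosed at Grade 1.* The footnote alone suggests so, but the resumption criteria above the table require return to baseline.
- *That the delay rule in 8.5, "8 weeks from the previous dose requires discontinuation", contradicts the table's 12 weeks.* One counts from the last dose and the other counts persistence of the reaction, so both can be obeyed.
- *That the 28 cycles in 8.3 conflict with two years of treatment.* Section 9 sets up to two years whatever the cycle count.

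**Conclusion.** The concern holds in the three places described, and the text should be changed. The table is laxer than 8.5 for Grade 3 colitis, for a first other Grade 3 reaction lasting more than 7 days, and for Grade 3 uveitis, bronchospasm or hypersensitivity of any duration. It is stricter for controlled Grade 3 adrenal insufficiency and for the Grade 4 events that 8.5 excepts. Section 11.2 is wider than 13.3, chiefly for progression after month 6.

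It would go too far to say that the protocol gives no indication of precedence, or that the conflict undermines the primary analysis. Section 6.9 gives an indication, and the sample size and response-rate test do not depend on these rules.

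The conclusion assumes that an event the table does not name falls in its other-Grade-3 row. Treating hypophysitis as covered by the Grade 4 endocrine exception is also an inference, because 8.5 does not name it. That sites would act differently is an inference too. The content of Appendix 1, which holds the toxicity algorithms, is not in the copy reviewed, and it could bear on the toxicity rows.

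**What to change.** **Section 9.** State that the mandatory stops and listed exceptions in 8.5 govern wherever the table differs. Then:
- Colitis and other-Grade-3 rows: add *permanently discontinue if Grade 3 lasts >7 days (see 8.5)*.
- Other-Grade-3 row: also add *at any duration for uveitis, bronchospasm, hypersensitivity or infusion reaction (see 8.2, 8.5)*.
- Adrenal row: except Grade 3 cases controlled with physiologic hormone replacement alone, which may resume after consultation with the principal investigator.
- Grade 4 rows, including the general one: make them subject to the exceptions in 8.5.

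**Section 11.2.** Make it subject to the 6-month limit and the 3-month confirmation window in 13.3. If the medical lead intends the wider permission, amend 6.9 and 13.3 to cite 11.2 instead.

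**Cost.** Wording in one protocol amendment and a memo to the three sites, once the medical lead has confirmed the intended rules. No added procedures, visits or participants.
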